#### **Reporting in eCRF**

The disease severity assessment score will be recorded in the eCRF. Refer to Appendix 1 (Section 12.1.8) for principles for data entry in the eCRF.

THIS DOCUMENT CONTAINS CONFIDENTIAL INFORMATION AND MUST NOT BE COPIED OR MADE AVAILABLE TO ANY THIRD PARTY WITHOUT THE PRIOR WRITTEN CONSENT OF THE LEO PHARMA GROUP

## Panel 9: vIGA-AD

Score	Morphological description
0 - Clear	No inflammatory signs of AD (no erythema, no induration/papulation, no lichenification, no oozing/crusting). Post-inflammatory hyperpigmentation and/or hypopigmentation may be present.
1 - Almost clear	Barely perceptible erythema, and barely perceptible induration/papulation, and/or minimal lichenification. No oozing or crusting.
2 - Mild	Slight but definite erythema (pink), slight but definite induration/papulation, and/or slight but definite lichenification. No oozing or crusting.
3 - Moderate	Clearly perceptible erythema (dull red), clearly perceptible induration/papulation, and/or clearly perceptible lichenification. Oozing and crusting may be present.
4 - Severe	Marked erythema (deep or bright red), marked induration/papulation, and/or marked lichenification. Disease is widespread in extent. Oozing or crusting may be present.

**Abbreviations:** AD = atopic dermatitis; vIGA-AD = validated Investigator Global Assessment Scale for Atopic Dermatitis.

### 8.3.4 BSA involvement

The total BSA affected by AD will be assessed by the investigator for each section of the body as component A of SCORAD (Section 8.3.2) and will be reported as a percentage of all major body sections combined. The following body regions will be assessed (brackets show the highest possible score for each region): head and neck (9%), anterior trunk (18%), back (18%), upper limbs (18%), lower limbs (36%), and genitals (1%). The total BSA score will be assessed according to the schedule of activities (Section 1.3).

The investigator will assess the total AD involvement for the whole body, i.e. head/neck, upper limbs, trunk, genitalia, and lower limbs, as a percentage of the total BSA. As a guidance for this estimate, the surface of a full, flat palm (including the 5 fingers) of an adult subject corresponds to approximately 1% of the total BSA.

### Reporting in eCRF

BSA involvement will be recorded as part of the SCORAD assessment. Refer to Appendix 1 (Section 12.1.8) for principles for data entry in the eCRF.

### 8.3.5 PROs

#### 8.3.5.1 Overview

During the trial, each subject should make individual assessments relating to their perception of their disease and quality of life. These should be performed independently of the investigator. At the screening visit (at the earliest Week -4), the subject's eligibility to participate in the trial needs to be established before the PROs can be completed.

THIS DOCUMENT CONTAINS CONFIDENTIAL INFORMATION AND MUST NOT BE COPIED OR MADE AVAILABLE TO ANY THIRD PARTY WITHOUT THE PRIOR WRITTEN CONSENT OF THE LEO PHARMA GROUP

The subject will be asked to complete PROs according to the schedule of trial activities (Section 1.3). PROs will either be completed at home (eDiary) or at the trial site (electronic device) (Panel 10).

### Panel 10: Overview of PROs to be completed

PROs to be completed at home (eDiary)	PROs to be completed at the trial site (electronic device)

To be completed in the morninga)
 
Nocturnal [REDACTED] (Section 8.3.5.2)
 
Difficulty [REDACTED] (Section 8.3.5.3)
 
Frequency of [REDACTED] During the Night (Section 8.3.5.4)
 
To be completed in the eveninga)
 
ADSD (all components) (Section 8.3.5.5)
	
DLQI (Section 8.3.5.6)
 
POEM (Section 8.3.5.7)
 
EQ-5D-5L (Section 8.3.5.8)
 
WPAI-SHP (Section 8.3.5.9)
 
HADS (Section 8.3.5.10)
 
PGI-S (Section 8.3.5.11)
 
[REDACTED]
 
ADSD
 
Nocturnal [REDACTED]
 
Difficulty [REDACTED]
 
Frequency of [REDACTED] During the Night
 
PGI-C (Section 8.3.5.12)
 
[REDACTED]
 
ADSD
 
Nocturnal [REDACTED]
 
Difficulty [REDACTED]
 
Frequency of [REDACTED] During the Night

a) The morning assessments will only be completed until Week 16, the evening assessments will be completed until Week 32.

**Abbreviations:** ADSD = Atopic Dermatitis Symptom Diary; DLQI = Dermatology Life Quality Index; eDiary = electronic diary; EQ-5D-5L = EuroQol 5-Dimension Health Questionnaire 5 Level; HADS = Hospital Anxiety and Depression Scale; PGI-C = Patient Global Impression of Change; PGI-S = Patient Global Impression of Severity; POEM = Patient-Oriented Eczema Measure; PRO = patient-reported outcome; WPAI-SHP = Work Productivity and Activity Impairment: Specific Health Problem.

At the screening visit, the subjects will receive an eDiary device and training in using the device. The subjects must start completing the eDiary at least 1 week prior to baseline, but preferably from the date the subjects receive the eDiary. From Week -1 to Week 16, the subjects will be asked to complete the eDiary twice daily, once in the morning and once in the evening. After Week 16, up to Week 32, the subjects will be asked to complete the eDiary in the evening only (Panel 10).

THIS DOCUMENT CONTAINS CONFIDENTIAL INFORMATION AND MUST NOT BE COPIED OR MADE AVAILABLE TO ANY THIRD PARTY WITHOUT THE PRIOR WRITTEN CONSENT OF THE LEO PHARMA GROUP

Between Week -1 and Week 32, an e-mail notification alarm will inform the investigator/site staff about non-compliance with eDiary completion. In case of non-compliance, the investigator should remind the subject of the importance of completing the eDiary daily.

Subjects will be asked to return the eDiary at Week 32 or at their last visit in the trial.

#### **8.3.5.2 Nocturnal [REDACTED] (eDiary)**

Nocturnal [REDACTED] is a single item questionnaire designed developed by LEO Pharma to assess how much the subject [REDACTED] during the past night. It will be assessed on a 6-point categorical scale ('none of the night', 'a little of the night', 'some of the night', 'a lot of the night', 'all of the night', 'I don't know').

#### **8.3.5.3 Difficulty [REDACTED] (eDiary)**

Difficulty [REDACTED] is a single item questionnaire designed developed by LEO Pharma to assess the subject's difficulty to [REDACTED] the past night. It will be assessed on a 5-point categorical scale ('not difficult', 'a little difficult', 'moderately difficult', 'extremely difficult', 'I don't know').

#### **8.3.5.4 Frequency of [REDACTED] During the Night (eDiary)**

Frequency of [REDACTED] During the Night is a single item questionnaire designed developed by LEO Pharma to assess how many times the subject [REDACTED] the past night. It will be assessed on a 5-point categorical scale ('not at all', '[REDACTED] 1 time', '[REDACTED] 2 times', '[REDACTED] 3 times or more', 'I don't know').

#### **8.3.5.5 ADSD (eDiary)**

ADSD is considered a subject's assessment of efficacy. ADSD is a 9-item sign and symptom diary developed by LEO Pharma. It assesses the severity of [REDACTED] [REDACTED]. The subject assesses the severity of each symptom 'at its worst' over the past 24 hours using an 11-point numeric rating scale, with anchors at 0='no [symptom]' and 10='worst possible [symptom]'.

From Week -1 to Week 32, ADSD will be completed by the subject on the eDiary daily. An overview of all PROs, including other PROs collected in the eDiary and PROs collected at the trial site, is presented in Section 8.3.5.1.

#### **8.3.5.6 DLQI (at trial site)**

DLQI consists of 10 items addressing the subject's perception of the impact of their skin disease on different aspects of their quality of life over the past week such as dermatology

related symptoms and feelings, daily activities, leisure, work or school, personal relationships, and the treatment. Each item will be scored on a 4 point Likert scale (0='not at all/not relevant', 1='a little', 2='a lot', 3='very much'). The total score (0 to 30) is the sum of the 10 items with higher scores indicating a poorer quality of life (72). The subject will be asked to complete DLQI on an electronic device at the trial site according to the schedule of trial activities (Section 1.3).

#### **8.3.5.7 POEM (at trial site)**

POEM consists of 7 items, each addressing a specific symptom (itching, sleep, bleeding, weeping, cracking, flaking, and dryness). The subject will be asked to score how often they experienced each symptom over the past week on a 5 point categorical scale (0='no days', 1='1 to 2 days', 2='3 to 4 days', 3='5 to 6 days', 4='every day'). The total score (0 to 28) is the sum of the 7 items and reflects disease related morbidity with higher scores indicating more severe symptoms (73). The subject will be asked to complete POEM on an electronic device at the trial site according to the schedule of trial activities (Section 1.3).

#### **8.3.5.8 EQ-5D-5L (at trial site)**

EQ-5D-5L is a self-administered questionnaire used to assess health status 'today' and is divided into 2 sections. The first section includes 5 dimensions (mobility, self-care, usual activity, pain/discomfort, and anxiety/depression). Each dimension is assessed using a 5-point categorical scale ('no problems', 'slight problems', 'moderate problems', 'severe problems', and 'extreme problems'). The second section consists of a vertical VAS anchored at 0 ('the worst health you can imagine') and 100 ('the best health you can imagine') (74). The subject will be asked to complete EQ-5D-5L on an electronic device at the trial site according to the schedule of trial activities (Section 1.3).

#### **8.3.5.9 WPAI-SHP (at trial site)**

WPAI-SHP (v2.0) consists of 6 items and scores can be calculated for 4 domains, each reflecting the percentage impairment due to AD during the past week, with higher scores indicating a greater impairment and lesser productivity (75):

- Absenteeism: percentage work time missed due to AD for those who were employed the past week.
- Presenteeism: percentage impairment while working due to AD for those who were employed and actually worked the past week.
- Work productivity loss: percentage overall work impairment due to AD for those who were employed the past week.
- Activity impairment: percentage activity impairment due to AD for all respondents.

THIS DOCUMENT CONTAINS CONFIDENTIAL INFORMATION AND MUST NOT BE COPIED OR MADE AVAILABLE TO ANY THIRD PARTY WITHOUT THE PRIOR WRITTEN CONSENT OF THE LEO PHARMA GROUP

The subject will be asked to complete WPAI-SHP on an electronic device at the trial site according to the schedule of trial activities (Section 1.3).

### 8.3.5.10 HADS (at trial site)

HADS is a 14-item questionnaire with scores ranging from 0 to 21 for anxiety and 0 to 21 for depression. Each of the 14 items will be evaluated on a Likert scale. Scores are considered normal from 0 to 7 and abnormal from 11 to 21 and are categorized as: normal (0 to 7), mild (8 to 10), moderate (11 to 14), and severe (15 to 21) (76). The subject will be asked to complete HADS on an electronic device at the trial site according to the schedule of trial activities (Section 1.3). If the subject presents with symptoms of clinical depression and/or anxiety, the investigator should take appropriate action at their discretion.

### 8.3.5.11 PGI-S (at trial site)

PGI-S is a questionnaire designed to assess the subject's overall perception of severity. In this trial the severity of [REDACTED], ADSD, nocturnal [REDACTED], difficulty [REDACTED], and frequency of [REDACTED] during the night over the past week will be evaluated. The subject will be asked to choose 1 option from a 4-point categorical scale as described in Panel 11 (77). The subject will be asked to complete the PGI-S questionnaire on an electronic device at the trial site according to the schedule of trial activities (Section 1.3).

#### Panel 11: PGI-S

PGI-S	Scale
[REDACTED]	'None', 'mild', 'moderate', 'severe'
ADSD	
Nocturnal [REDACTED]	
Difficulty [REDACTED]	
Frequency of [REDACTED] During the Night PGI-S	'Never', 'sometimes', 'often', 'very often'

**Abbreviations:** ADSD = atopic dermatitis symptom diary; PGI-S = Patient's Global Impression of Severity.

### 8.3.5.12 PGI-C (at trial site)

PGI-C is a questionnaire designed to assess the subject's overall impression of change. In this trial the change in [REDACTED], ADSD, nocturnal [REDACTED], difficulty [REDACTED], and frequency of [REDACTED] during the night since the subject started treatment will be evaluated. The subject will be asked to choose 1 option from a 5 point categorical scale ('much better', 'a little better', 'no change', 'a little worse', 'much worse') (77). The subject will be asked to complete the PGI-C questionnaire on an electronic device at the trial site according to the schedule of trial activities (Section 1.3).

THIS DOCUMENT CONTAINS CONFIDENTIAL INFORMATION AND MUST NOT BE COPIED OR MADE AVAILABLE TO ANY THIRD PARTY WITHOUT THE PRIOR WRITTEN CONSENT OF THE LEO PHARMA GROUP

## 8.4 Safety assessments

Planned timepoints for all safety assessments are provided in the schedule of activities ([Panel 2](#)).

### 8.4.1 Vital signs

Vital signs (resting BP, pulse, and body temperature) must be assessed prior to IMP administration according to the schedule of trial activities (Section [1.3](#)). Vital signs will be measured in a supine or sitting position following at least 5 minutes of rest, and will include resting blood pressure, pulse, and body temperature. At an unscheduled visit, it will be at the discretion of the investigator if vital signs should be assessed.

In addition, at Weeks 0, 1, 2, 3, and 4, subjects will be monitored after IMP administration for immediate drug reactions for a minimum of 2 hours with vital signs taken immediately (within 5 minutes) after last IMP administration, after 30 minutes ( $\pm$  5 minutes), after 1 hour ( $\pm$  5 minutes), and after 2 hours ( $\pm$  5 minutes), or until stable, whichever is later (**for requirements specific for EU countries i.e. CZ, DE, ES, FR, HU, PL and RO, see Section [12.5.1](#)**).

If a subject presents with an abnormal vital sign, the measurement of the vital sign can be repeated approximately 15 minutes later to verify the first measurement. Should the repeated measurement result in a normal value, the measurement must be repeated once more. If the third measurement verifies the second normal value, the first measurement should be considered false and the second measurement should be recorded in the eCRF. If the third measurement confirms the first measurement abnormal, the second measurement should be considered false and the first measurement should be recorded in the eCRF. Only the measurement considered true should be recorded in the eCRF, but note that all measured values should be documented in source in these scenarios.

In case of a clinically significant abnormal vital sign at screening and/or baseline, it will be at the discretion of the investigator if the subject should be included in the trial in accordance with exclusion criterion no. [15](#). During the trial, if a subject presents with a clinically significant abnormal vital sign, the investigator must take appropriate action, at their discretion.

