### **After IMP administration**

At Weeks 0, 1, 2, 3, and 4, subjects will be monitored for potential immediate drug reactions for a minimum of 2 hours after IMP administration. Vital signs will be taken immediately (within 5 minutes) after last IMP administration, as well as after 30 minutes ( $\pm$  5 minutes), after 1 hour ( $\pm$  5 minutes), and after 2 hours ( $\pm$  5 minutes), or until stable, whichever is later **(for requirements specific for EU countries i.e. CZ, DE, ES, FR, HU, PL and RO, see Section 12.5.1)**. Vital signs will be documented in the eCRF.

As with any Ab, allergic reactions to dose administration are possible. The World Allergy Organization has categorized anaphylaxis into 2 subgroups: allergic anaphylaxis (mediated by an immunologic mechanism) and nonallergic anaphylaxis (which has a nonimmunologic cause) (64). The clinical criteria for defining anaphylaxis for this trial are listed in Appendix 4 (Section 12.4) and (65). Appropriate drugs, such as epinephrine, antihistamines, corticosteroids, etc., and medical equipment to treat acute anaphylactic reactions must be immediately available at trial sites, and trial personnel should be trained to recognize and respond to anaphylaxis according to local guidelines.

If an anaphylactic reaction occurs, a blood sample will be drawn from the subject 1) as soon as possible after the event, 2) at 60 minutes ( $\pm$  30 minutes) after the event, and 3) at discharge for analysis of serum tryptase at the central laboratory.

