#### **11.3.13.2 Vital signs**

The change in vital signs (resting BP, pulse, and body temperature) from baseline to each relevant visit will be summarized as mean, SD, median, minimum, and maximum values for each treatment group. Shift table for clinically significant abnormal vital signs will be presented.

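### The repeat-and-replace rule for vital signs is not limited to pre-dose readings, so it can remove transient post-injection abnormalities from the eCRF

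*Combined protocol and SAP*

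**What the plan says.** Section 8.4.1 requires vital signs before each administration on the schedule. At Weeks 0, 1, 2, 3 and 4 it adds post-injection sets within 5 minutes and at 30 minutes, 1 hour and 2 hours (each ±5 minutes), continued until stable if that takes longer. Section 6.2 gives the purpose: "subjects will be monitored for potential immediate drug reactions for a minimum of 2 hours after IMP administration". It adds that these vital signs go into the eCRF. For EU sites, Section 12.5.1 adds sets within 5 minutes and at 20 minutes (±5 minutes) at the later dosing visits.

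The paragraph of Section 8.4.1 directly after the post-injection schedule gives a rule for any abnormal vital sign:

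- First repeat: "the measurement of the vital sign can be repeated approximately 15 minutes later to verify the first measurement".
- Third reading: "Should the repeated measurement result in a normal value, the measurement must be repeated once more".
- If the third is normal: "If the third measurement verifies the second normal value, the first measurement should be considered false and the second measurement should be recorded".
- If the third is abnormal, the second is treated as false and the first is entered.
- What is kept: "Only the measurement considered true should be recorded in the eCRF, but note that all measured values should be documented in source in these scenarios".

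For analysis, Section 11.3.13.2 plans summaries of change from baseline to each relevant visit, and "Shift table for clinically significant abnormal vital signs will be presented".

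**The concern.** For a single resting measurement, two normal repeats are fair evidence that the first reading was an artefact. After an injection the same sequence has a second explanation: a reaction that began and resolved. The rule cannot tell these apart, yet it tells the site to treat the first reading as false and to enter a later normal one. The monitoring exists to find immediate reactions, and the recording rule can remove the short ones from the data set.

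What is at stake is the completeness of the post-dose safety record. Abnormal readings of no individual clinical significance are where a difference between arms might first show, and they have no other route into the data. The synopsis states that there is no DMC, so review of collected safety data by the sponsor's own personnel (Section 2.4) carries more weight. Because the first repeat is optional, sites may also record the same sequence differently.

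**Working it through.** The plan gives no figure to reproduce. The check is a reading of the text, a comparison of time windows and a count of exposed readings.

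**1. Does the rule reach post-dose readings?** Its trigger is a subject presenting with an abnormal vital sign, with no qualifier. The next paragraph of Section 8.4.1 does name screening and baseline where it means only those visits. No exemption or separate repeat rule for post-dose readings appears in Section 6.2, in footnote o of Panels 2 and 18, or in the EU text of Section 12.5.1. Coverage therefore follows from general wording without an exemption, not from an explicit statement.

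**2. When is the replacement value taken?** Time of repeat = time of first reading + about 15 minutes.

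| Slot | Allowed window (min) | Repeat taken at about (min) | Past the end of the window by (min) |
|---|---|---|---|
| Within 5 min | 0–5 | 15–20 | 10–15 |
| 30 min | 25–35 | 40–50 | 5–15 |
| 1 h | 55–65 | 70–80 | 5–15 |
| 2 h | 115–125 | 130–140 | 5–15 |

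At every slot the recorded value falls outside the window. At EU sites after Week 4, the repeat of the first post-dose reading (15–20 minutes) falls inside the window of the scheduled 20-minute set (15–25 minutes).

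**3. What happens in each sequence?**

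| First | Second | Third | Entered in eCRF |
|---|---|---|---|
| Abnormal | Not taken | – | First (abnormal); the replacement rule is not reached |
| Abnormal | Normal | Normal | Second (normal), in place of the first |
| Abnormal | Normal | Abnormal | First (abnormal) |

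A value is lost only in the middle row, and there the replacement is always normal for abnormal. An abnormality that resolves in under about 15 minutes and stays resolved lands in that row whenever the site repeats.

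**4. How many readings are exposed?** The counts come from Panels 2 and 18 for a subject who receives every dose.

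- Non-EU post-dose: 5 visits × 4 = 20 sets. Pre-dose at dosing visits with vital signs (Weeks 0, 1, 2, 3, 4, 8, 12): 7 sets. Share post-dose: 20/27 = 74%.
- EU post-dose: 20 + 5 visits (Weeks 6, 8, 10, 12, 14) × 2 = 30 sets. Pre-dose: 10 sets. Share post-dose: 30/40 = 75%.
- Weeks 0–4, all 250 subjects: 20 × 250 = 5,000 sets.

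These are denominators. The documents give no rate of abnormal readings, of optional repeats or of the abnormal–normal–normal sequence, so the number replaced cannot be derived.

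**The case against.** The strongest reply is that the rule was written for single resting readings and that post-dose readings have their own regime: fixed times, narrow windows and continuation until stable, which treats instability as real. A 15-minute repeat does not fit a 5-minute slot, which suggests nobody meant it to. That is plausible as intent, but the text does not say so, and a site following it literally would replace the value.

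Other parts of the reply stand and limit the point:

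- **The first repeat is optional.** Without it the abnormal value stays, and a later normal scheduled reading does not overwrite it. A reader might infer automatic replacement; the documents do not support that.
- **Post-dose readings are serial.** A normal first reading is followed by further scheduled ones, and the abnormal–normal–abnormal branch keeps the abnormal value. It would be wrong to say that a missed abnormality can never be recovered, or that the whole rule works in one direction.
- **Section 6.2 does not contradict Section 8.4.1.** One says that vital signs are entered, the other says which value. A site can comply with both.
- **Other routes remain.** Every value is kept in source, and under Section 8.4.1 a new clinically significant abnormality must be reported as an AE, with no exception for readings that normalize. Anaphylaxis has its own clinical criteria (Section 12.4) and tryptase sampling (Section 6.2). Still, the AE route asks the investigator to judge significant a value that the protocol says to consider false.

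**Conclusion.** The point holds in a limited form. As written, Section 8.4.1 lets a true but brief post-injection abnormality be recorded as a normal value taken outside its slot. This requires that the site uses the optional repeat and that the second and third readings are both normal. The main loss is from the eCRF only: transient abnormalities judged not clinically significant, or discounted because of the rule's own label.

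A reader might infer that the vital-sign tables will be biased toward no post-dose effect in the active arms. The documents do not show this. Section 11.3.13.2 does not say whether post-dose readings enter the summaries or the shift table, and the rule applies alike in all arms. If brief reactions are drug-related, more readings would be removed in the active arms, but that is an assumption. The 20 sets per fully dosed subject (30 in the EU) measure exposure to the rule, not readings lost, and neither does 5,000 sets measure a loss.

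The primary endpoint is not affected. The matter concerns the completeness of safety data and is worth correcting because the correction is cheap.

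**What to change.** - In Section 8.4.1, and in the EU text of Section 12.5.1, limit the repeat-and-replace rule to pre-dose readings and readings at visits without dosing.
- For each post-dose time point, enter the first reading and every repeat in the eCRF with actual clock times. State that a later normal value does not by itself make a post-dose reading false.
- In Section 11.3.13.2, state whether post-dose readings enter the summaries and the shift table, and which reading represents a time point when there are several.

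The cost is protocol wording and extra timed fields in the eCRF. No new measurement is needed, because all values are already kept in source. A few spurious abnormal readings will stay in the data, visible beside their repeats. The change concerns recording and reporting only; it does not alter how subjects are monitored or managed.
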